	
 
Progestogens that are pregnadien derivates (including medroxyprogesterone and medroxyprogesterone alone)
 

	- Progestogen and oestrogen combination products.
	Objective 4: Same as Objective 2.
	Objective 5: Same as Objective 2.
	Objective 6: N/A
Comparator:	Before vs. After the implementation of restrictions
Outcome:	Objective 1: Prescribing of drug classes of interest (assessed separately)
	Objective 2: N/A (treatment duration and cumulative use of the exposure).
	Objective 3: N/A (characterisation of users)
	Objective 4: Prescribing of alternative treatments not containing NOMAC or CMA (assessed retrospectively to identify line of treatment).
	Objective 5: Number of patients diagnosed with meningioma during treatment and number of patients discontinuing treatment or switching to alternative treatments not containing NOMAC or CMA 180 days after the end of the index treatment.
	Objective 6: Prescribing of products containing NOMAC or CMA (assessed separately).
Time:	01/01/2010 to end of data availability
Setting:	Routinely collected data from 3 databases in 3 European countries.
Main measure of effect:	Objective 1:
	Incidence rates (new prescriptions per 100,000 person-years of the population at risk) and prevalence (proportions).
	Objective 2 to 5:
	- Objective 2: Median with minimum, maximum and interquartile range.
	- Objective 3-5: Counts and proportions
	
 
All objectives: Standardised Mean Differences (SMD) for comparing changes before and after the implementation of restrictions.
 

	Objective 6:
	Risk ratios derived from the interrupted time series analysis (ITS). ITS will be based on results obtained as part of Objective 1.

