#### IQVIA Belgium Longitudinal Patient Data (IQVIA LPD), Germany

Belgium Longitudinal patient data (LPD) is collected from GP prescribing systems and contains patient records on all signs and symptoms, diagnoses and prescribed medications. The information recorded allows patients and doctors to be monitored longitudinally. Data are recorded directly in the LPD from doctors' surgeries in real-time during patient consultations via a practice management software system. It is used in studies to provide various market insights such as treatment trends, patient pathway analysis and treatment compliance. The panel of contributing physicians (a stable 300 GPs) is maintained as a representative sample of the primary care physician population in Belgium according to three criteria known to influence prescribing: age, sex and geographical distribution. Currently, the database is covering 1.1 M cumulative patients and covers from 2012 through to the present. The panel consists of a stable 300 GPs that are geographically well spread. The total number of active GPs in Belgium is 15.602. The regional geographical spread of physicians in the LPD data is also representative of the distribution across the country: 57% GPs in the North (compared to 54% nationally), 31% in the South (33% nationally) and 12% in Brussels (13%). The provider of the data has more than 2.250 GPs under contract so in case of a drop out a replacement is easily found. Drugs obtained over the counter by the patient outside the prescription system are not reported. No explicit registration or approval is necessary for drug utilisation studies.

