#### Objective 6:

The impact of the restrictions of use will be estimated using an ITS. This analysis will be restricted to NOMAC and CMA (assessed separately) and will be informed by results of the main analysis obtained as part of objective 1 (no meningioma restriction). For NOMAC, the intervention taken place in 2018 will also be assessed.

Time series will be assessed using segmented regression. Monthly incident counts of patients prescribed with NOMAC or CMA will be modelled using a Poisson regression model. Quasi-Poisson models will be considered in the presence of overdispersion. The effect size of the intervention will be estimated using risk ratios (RR).

The assumption of linearity will be assessed by visually inspecting the data and residuals, as well as through statistical goodness-of-fit tests. Autocorrelation will be assessed by examining the plot of residuals and the partial autocorrelation function and conducting statistical tests where possible. If seasonality is detected, it will be controlled for by including variables representing them in the regression model. If the trends are not (or cannot be transformed to be linear) or in the presence of residual autocorrelation, ITS will not be conducted due to the complexity of predicting the counterfactual and to disentangle the intervention effects.(23)

Authors: [name], [name], [name], [name], [name]

Version: V4.0

Dissemination level: Public

The impact model of the intervention (i.e. how we expect the intervention has impacted the outcome) is anticipated to show an abrupt change in the level and a gradual change in the gradient of the trend (step and slope change). Potential impact models will be further discussed and agreed with EMA and defined a priori.(23, 24)

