#### A. Primary analysis

Hypothesis:	Objective 1: Not applicable, descriptive analysis.
	Objective 2: Cumulative dose and duration of treatments with NOMAC or CMA will be lower after the implementation of restrictions.
	Objective 3: The number of new users of NOMAC or CMA with prior history of meningioma will be reduced after the implementation of restrictions.
	Objective 4: The number of users initiating NOMAC or CMA as first-line treatment will be reduced after the implementation of restrictions.
	Objective 5: The number of discontinuations and switches from NOMAC or CMA to other drug classes will increase after the implementation of restrictions.
	Objective 6: The incidence of NOMAC or CMA will be reduced after the implementation of restrictions, especially for high-dose products. This reduction will not be observed for other drug classes of interest.
Exposure contrast:	Objective 1: Not applicable, descriptive analysis.
	Objective 2: Pre-intervention (1-year period) vs. Post-intervention (1-year period)
	Objective 3 to 6: Pre-intervention vs. Post-intervention
Outcome:	Objective 1: Incidence rates and prevalence of drug classes of interest
	Objective 2: Cumulative dose and treatment duration of NOMAC or CMA.

Authors: [name], [name], [name], [name], [name]

Version: V4.0

Dissemination level: Public

	Objective 3: Number and characteristics of users of drug classes of interest.
	Objective 4: Line of treatment when initiating NOMAC or CMA.
	Objective 5: Diagnosis with meningioma during treatment. Discontinuations and switches
	from treatments with NOMAC or CMA to others.
	Objective 6: Incidence rates of NOMAC or CMA.
	Drug classes of interest, NOMAC and CMA will be assessed separately.
Analytic software:	R
Model(s):	Objective 1: Not applicable, descriptive analysis.
	Objective 2 to 5: Standardised mean differences.
	Objective 6: Segmented regression (Poisson models).
Confounding adjustment method	
	Stratification.
Missing data methods	
	The absence of a record for a condition or medication will be considered as the absence of the disease or use of the medication.
Subgroup Analyses	
	Objective 1: Age groups, indication, study period. For NOMAC or CMA only: dose, WHO ATC 5 th level (if counts allow). A subgroup analysis will be performed restricting the study population to individuals with a prior history of meningioma.
	Objective 2: Study population, indication, study period.
	Objective 3: Study period.

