#### **Databases:**

In IQVIA LPD Belgium and IQVIA DA Germany, the observation period of the patients in these databases is calculated based on the last visit, observation or interaction of the patient with the health care system. This methodology impacts the individuals considered "at risk" for the different medicines of interest of the study (i.e., the individuals included in the denominator populations) during the latest months of available data from the latest data lock, where healthy and/or non-frequent users of the health care system will not be considered active. Consequently, the denominators that will be used to calculate the incident use of drugs in the population may present an artefactual decrease whilst the incident users will remain, incrementing the incidence and prevalence ratios. The presence of these artefacts will be considered when interpreting the results. However, this is likely to affect the amount of follow up available for the study. We expect that the data from the last 6 months may not accurately reflect actual figures of use and, therefore, will be excluded from the analysis for Objective 1 and 6.

Regarding the study period, NAJS will provide data from 2017 onwards only, as prior data might include information on duplicated patients. IQVIA LPD Belgium will provide data from 2012 onwards.

Since information on drug exposure end dates is unavailable in NAJS, treatment duration will not be inferred directly from the start and end dates of drug exposure. Instead, we will infer the treatment period using only the drug exposure start dates, assuming continuous drug exposure between consecutive start dates, if separated by less than 90 days. To account for the final prescription, we apply a 30-day window following the last recorded drug start date. This approach might lead to some uncertainty regarding the exact duration or cumulative dose prescribed.

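### The six-month IQVIA cut is applied to Objective 6 for a denominator reason, while section 8.8 models counts and Table 11 names rates; under the cut Germany keeps 2 of 8 post-intervention months

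*Protocol*

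**What the plan says.** Section 11 (Databases) explains that in IQVIA DA Germany and IQVIA LPD Belgium a patient's observation period ends at the last recorded interaction. Near the data lock the denominators "may present an artefactual decrease whilst the incident users will remain, incrementing the incidence and prevalence ratios". It continues: "We expect that the data from the last 6 months may not accurately reflect actual figures of use", and these months "will be excluded from the analysis for Objective 1 and 6".

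On what Objective 6 analyses, the protocol says different things in different places:

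- Section 8.8, Objective 6: "Monthly incident counts of patients prescribed with NOMAC or CMA will be modelled using a Poisson regression model". No offset or person-time term is named. The expected impact is a step and a change in slope.
- Table 11, outcome row: "Objective 6: Incidence rates of NOMAC or CMA".
- Table 1, main measure of effect: "ITS will be based on results obtained as part of Objective 1". Section 8.8 defines the Objective 1 incidence measure as a rate per 100,000 person-years.
- Section 8.4 gives Objective 6 the same follow-up as Objective 1.

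For the 2022 measures the series starts in January 2021, November 2022 to January 2023 is removed as a transition period, and the post-intervention period starts in February 2023. Table 3 gives data locks of 30-09-2023 (Germany) and 31-12-2023 (Belgium).

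**The concern.** The artefact in section 11 acts on the denominator. Its own description is that the denominators "may present an artefactual decrease whilst the incident users will remain". A new prescription is itself an interaction, so it falls inside an observation period that ends at the last interaction. A model of monthly counts without an offset, as section 8.8 words it, therefore does not inherit the artefact, and section 11 describes no defect in the numerator. A model of rates does inherit it.

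Whether the cut belongs in Objective 6 thus depends on a choice that the protocol makes in two ways. Post-intervention months are the scarcest information in the study. Section 8.7 says that unbalanced series lose power and delays the series start to balance the observations; the cut works against that aim. Section 8.8 also makes acceptable linearity and the absence of residual autocorrelation conditions for running the analysis, and these can hardly be checked after the intervention when very few points remain.

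**Working it through.** The protocol gives no power or precision figure of its own for Objective 6, so there is none to reproduce.

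**Months (Table 3 locks; sections 8.6.3, 8.8 and 11)**

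- Pre-intervention: January 2021 to October 2022 = 22 months.
- Germany, post: February to September 2023 = 8; minus 6 = 2 (February and March 2023).
- Belgium, post: February to December 2023 = 11; minus 6 = 5 (February to June 2023).
- Splits with the cut are 22:2 and 22:5; without it 22:8 and 22:11.

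**Standard errors, in units of the monthly residual SD**

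The model has intercept, trend, step at February 2023 and slope change, with equal weights and independent residuals. For m equally spaced months, S(m) = m(m² − 1)/12, so S(22) = 885.5, S(2) = 0.5, S(5) = 10, S(8) = 42 and S(11) = 110.

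Slope change: SE = √[1/S(22) + 1/S(m)].

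Step: with pre months numbered 0 to 21 (mean 10.5) and February 2023 as month 25, the pre part is 1/22 + 14.5²/885.5 = 0.2829. The post part is 1/m + ((m − 1)/2)²/S(m).

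| | Post months | Slope-change SE | Step SE |
|---|---|---|---|
| Germany, cut | 2 | √(1/885.5 + 1/0.5) = 1.415 | √(0.2829 + 1.0000) = 1.133 |
| Germany, all | 8 | √(1/885.5 + 1/42) = 0.158 | √(0.2829 + 0.4167) = 0.836 |
| Belgium, cut | 5 | √(1/885.5 + 1/10) = 0.318 | √(0.2829 + 0.6000) = 0.940 |
| Belgium, all | 11 | √(1/885.5 + 1/110) = 0.101 | √(0.2829 + 0.3182) = 0.775 |

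Slope ratios: 1.415/0.158 = 9.0 and 0.318/0.101 = 3.1. Step reductions if the months are kept: 1 − 0.836/1.133 = 26% and 1 − 0.775/0.940 = 18%. With two German post points, the step and slope terms fit both exactly, so no post-intervention residual remains.

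**Illustration for Germany (assumed values)**

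Take σ = √(1.5/n) on the log scale, where n is the assumed number of starters a month and 1.5 an assumed overdispersion. The 95% interval around a null monthly slope ratio is exp(±t·σ·SE), with t = 2.086 (20 df, cut) or 2.056 (26 df, all).

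| n | σ | Cut | All months |
|---|---|---|---|
| 20 | 0.274 | 0.45–2.24 | 0.92–1.09 |
| 50 | 0.173 | 0.60–1.67 | 0.95–1.06 |
| 200 | 0.087 | 0.77–1.29 | 0.97–1.03 |

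**If rates are modelled and the months are simply kept (assumed values)**

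Assume a true step risk ratio of 0.70, no true slope change, unchanged recording of starters, and person-time multiplied by 1 − L·k/6 in the k-th of the last six months (k = 1 to 6). Noise-free Poisson fits with a log person-time offset give:

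| Loss L in final month | Germany, step-only RR | Belgium, step-only RR | Germany, spurious monthly slope ratio | Belgium, spurious monthly slope ratio |
|---|---|---|---|---|
| 10% | 0.73 | 0.71 | 1.016 | 1.011 |
| 30% | 0.78 | 0.73 | 1.055 | 1.037 |
| 50% | 0.85 | 0.76 | 1.108 | 1.072 |

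The slope ratios come from the step-and-slope model. Without an offset the step-only estimate is 0.70 in each case.

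**The case against.** The strongest answer is that Objective 6 is a rate analysis. Table 11 says so, Table 1 builds the series on Objective 1, and Poisson regression of counts with a person-time offset is the usual way to model a rate. Section 8.8 names no offset but does not exclude one, and that detail may sit in the analysis plan. On this reading the cut is justified: keeping the months would bias the post-intervention rate upward and mask a reduction. This stands, and it rules out simply lifting the cut.

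A reader might infer that the protocol itself declares the Objective 6 counts unaffected and that the months are discarded needlessly. The text does not go that far. It says that incident users remain while denominators fall, then speaks more broadly of actual use and names Objective 6 explicitly. That the counts escape the artefact is an inference from the mechanism, and it holds only for a count model without last-visit person-time.

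Numerator completeness is also only partly documented. Section 8.2 says that Belgian records are entered "in real-time during patient consultations via a practice management software system"; for Germany it mentions only regular routine updates. A pure count model cannot separate a change in panel size from a change in prescribing.

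Section 11 does concede that follow-up will be affected, and section 8.8 allows the amount of pre-intervention data or the frequency of data points to be adjusted. Neither provision supplies a reason for applying the cut to a count model, or adds post-intervention months.

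**Conclusion.** The point holds as an unresolved conflict with a material cost. If section 8.8 is followed as worded, the reason in section 11 does not support the cut for Objective 6. If Table 11 is followed, the cut has a reason, but the offset should be stated.

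Either way, applying the cut leaves Germany, the largest database by active subjects, with two post-intervention points for a step-and-slope model. Its slope change is then practically inestimable. The loss for the step is modest.

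The month counts assume that the Table 3 locks are those used. Execution is planned for March/April 2025, and a later lock would add months. The six-month rule is read as applying to the two IQVIA databases only, as its paragraph implies. The standard error ratios assume equal weights and independent residuals. The intervals and the bias table rest on the assumed values shown.

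**What to change.** 1. Reconcile section 8.8, Table 11, Table 1 and section 11 on whether Objective 6 models counts or rates, and state the offset.
2. Keep the six-month exclusion for Objective 1 and for any Objective 6 model that uses last-visit person-time as its offset.
3. Also fit the Objective 6 count model through the last complete month before the lock (September 2023 in Germany and December 2023 in Belgium at the Table 3 locks). Use a month-length offset, or an offset from a denominator that does not depend on later contacts and is defined identically in every month, for example women with a contact in the preceding 365 days. Report this series beside the cut series.
4. If only the cut series is used, state that no slope change will be interpreted for Germany from two post-intervention points.

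The cost is a short text change and one further run on data already held. The downside is that late uploads or panel changes may lower the final months. Comparing the two series helps to show late-upload effects, but it does not by itself separate panel size from prescribing. A denominator based on preceding contacts also differs from the Objective 1 at-risk population, and the report should say so.

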## Objective 2:

Treatment duration will be reported for the first prescribed treatment. Duration will be derived from the start and end of the prescription.

Cumulative dose will be calculated considering all treatments containing NOMAC or CMA recorded during the study period. If two eras with different doses are separated by less than 30 days, the time between the two eras will be considered as exposed by the first era (Figure 1, first row). If two eras start at the same date, the overlapping period will be considered exposed by both.

[figure not shown]

Figure 1. Gap era joint mode

Cumulative dose and treatment duration will be calculated for all treatments initiated during the study period and occurring over one year before and after the intervention to compare time periods of equal duration. The pre-intervention period for comparison will span from October 2021 to September 2022,

Authors: [name], [name], [name], [name], [name]

Version: V4.0

Dissemination level: Public

the year prior the request for PRAC to review current evidence on NOMAC and CMA. The post-intervention period for comparison will span from February 2023 to January 2024. For databases with less available data (see Table 3) we will limit the comparison to 6 months (post-intervention: February to July 2023; pre-intervention: February to July 2022). Time periods for comparison will cover the same calendar months in case seasonality is detected.

NOMAC and CMA will be assessed separately. Results will be reported overall and stratified by study period (pre- vs. postintervention) and indication at first use (non-HRT vs. HRT).

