## Objective 5:

[figure not shown]
We will describe the number and proportion of patients that follow different treatment strategies in the 180 days following the end of treatment. These strategies are defined as:

- Restart the same treatment
- Switch to a different treatment
- Restart and switch to a different treatment
   Discontinued treatment (not treated, neither with the original treatment nor any potential switch)

For this objective (time period comparison), both incident and prevalent users will be considered. The proportion of individuals following each treatment strategy (e.g. switching) will be calculated using the number of people exposed to the product of interest during the time period under study (e.g. pre-intervention) as the denominator regardless of when the initiation started.

Figure 2 illustrates some of these scenarios.

**Figure 2.** Outcomes after the drug exposure of interest (in blue) over different time periods.

Source: DrugUtilisation R package website (22)

The number of meningioma cases occurring any time during treatment with NOMAC or CMA, and in the six months prior to the end of treatment will also be reported. For cases identified in the six months prior, we will report the treatment strategy followed after treatment (i.e. restart, switch, both, or discontinuation).

NOMAC and CMA will be assessed separately. Results will be reported overall and stratified by study period (pre- vs. postintervention) and WHO 5th ATC level codes (if counts allow). For the pre- and post-intervention comparison, treatments initiated during the 180 days before the intervention will not be considered, to ensure sufficient time for assessing outcomes (e.g., switches, discontinuations) prior to the intervention.

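### NAJS exposure rule: a 90-day joining limit with a fixed 30-day tail would understate treatment length for users on about three months' supply, and the protocol does not state this direction

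*Protocol*

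**What the plan says.** The rule is in protocol section 11, under Databases. It is needed because of a gap in the source: "Since information on drug exposure end dates is unavailable in NAJS". Episodes are built from start dates, "assuming continuous drug exposure between consecutive start dates, if separated by less than 90 days". The end of an episode is then fixed: "To account for the final prescription, we apply a 30-day window following the last recorded drug start date". The protocol's only comment on the consequence is "This approach might lead to some uncertainty regarding the exact duration or cumulative dose prescribed", with no direction or size.

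The rule feeds two objectives in section 8.8.

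- **Objective 2.** "Treatment duration will be reported for the first prescribed treatment". Cumulative dose is summed over all recorded NOMAC or CMA treatments. The objective has its own bridging rule, but that deals with a narrower case: "If two eras with different doses are separated by less than 30 days".
- **Objective 5.** What happens in the 180 days after treatment ends is put into categories, one of which is "Restart the same treatment". Meningioma is counted while treatment is running and in the six months before it ends.

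Table 3 gives NAJS feasibility counts of 1.9k for NOMAC and 15.3k for CMA (whole database, unrestricted) and a data lock of 17-11-2023. The ENCePP checklist in Appendix III marks item 10.8, on sensitivity analyses, as No.

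**The concern.** The joining limit tolerates almost three months between starts, yet a prescription with nothing after it within that limit is worth one month. For monthly supplies this does little harm. For supplies of about three months the result depends on which side of day 90 the refill falls: one day later, and a long continuous episode breaks into isolated 30-day pieces.

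Three NAJS results would then partly reflect supply length and refill timing rather than treatment length:

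- first-treatment duration in Objective 2, and cumulative dose if it is built from the inferred days;
- the split between restart and the other categories in Objective 5;
- meningioma on treatment, because a diagnosis after day 30 of a longer final supply falls after the recorded end of treatment.

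**Working it through.** The protocol states no derived figure here, so there is nothing to reproduce. The rule was applied literally.

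**Inputs from section 11:** join if the start-to-start interval is under 90 days (89 at most); add 30 days after the last start of each episode.

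**Assumed:** refill intervals and pack sizes, with use continuous from one fill to the next.

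**Formulas for n fills at interval k.** True days = n × k. If k ≤ 89: one episode of (n − 1) × k + 30 days. If k ≥ 90: n episodes of 30 days each.

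| Refill interval | Fills | True days | Episodes | First duration | Recorded days | Share |
|---|---|---|---|---|---|---|
| 30 | 12 | 360 | 1 | 360 | 11 × 30 + 30 = 360 | 100% |
| 84 | 4 | 336 | 1 | 282 | 3 × 84 + 30 = 282 | 83.9% |
| 89 | 4 | 356 | 1 | 297 | 3 × 89 + 30 = 297 | 83.4% |
| 90 | 4 | 360 | 4 | 30 | 4 × 30 = 120 | 33.3% |
| 91 | 4 | 364 | 4 | 30 | 4 × 30 = 120 | 33.0% |

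From 89 to 90 days, first-treatment duration falls from 297 to 30 days, a factor of 297/30 = 9.9.

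**Where a quarterly refill falls.** Of all calendar three-month intervals starting in 2017–2023, 93.2% are 90–92 days long (not joined) and 6.8% are 89 days (joined).

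**Irregular refills.** Simulated users had four fills with normally distributed intervals rounded to whole days. With a mean of 90 to 91.3 days and SD of 3 to 14 days, the mean recorded share is 46–55%, the median first duration is 30 days, and 52–73% of users have a first treatment of exactly 30 days. With a mean of 84 days and the same SDs, the mean share is 64–82%.

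**Opposite direction.** Two 28-day packs started 89 days apart are recorded as 89 + 30 = 119 days against 2 × 28 = 56 supplied, or 2.1 times.

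**Does the Objective 2 bridging rule repair it?** No. At a 91-day interval the false gap is 91 − 30 = 61 days. That rule covers gaps under 30 days between eras of different dose.

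**Shorter window.** With the Table 3 lock, NAJS cannot reach January 2024, so Objective 2 uses the six-month comparison (initiations February–July 2023). Follow-up to the lock is then 289 days for a start on 1 February and 109 days for a start on 31 July. A woman with two 91-day fills has 2 × 30 = 60 of 182 days recorded (33%); with two 89-day fills, 89 + 30 = 119 of 178 (67%).

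**Objective 5.** At a 91-day interval the next fill comes 61 days after the recorded end, inside the 180-day window, so a continuous user is classed as restarting. If her last supply lasts 90 days and she is diagnosed on days 31–90, the diagnosis follows the recorded end and lies outside both meningioma windows. This also applies to users whose earlier fills were joined, since the final record always gets 30 days.

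**The case against.** The strongest reply has five parts.

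1. **The refill pattern is not documented.** The protocol gives no NAJS pack sizes or intervals. One third is exact only if every interval is 90 days or slightly more; a three-pack supply of 28 days each lasts 84 days and is joined. This stands: the share of users affected is unknown.
2. **A short tail with a longer permitted gap is an ordinary grace-period rule.** This stands too. A reader might infer that the two constants contradict each other; the text does not say that one prescription covers 89 days, so there is no contradiction. The choice can be questioned, but it is not an inconsistency.
3. **The limitation is disclosed.** Only in part. The caveat covers duration and cumulative dose but gives no direction, and it does not mention restarts or on-treatment meningioma.
4. **The comparison is before versus after within each database, without pooling.** The same constants apply in both periods and create no difference by themselves. This stands.
5. **The stakes are modest.** The feasibility counts are unrestricted, the Objective 2 comparison uses only 6–12 months of initiations, and section 8.8 compares discontinuation, switching and meningioma between periods, not restart. Section 11 also expects few meningioma cases. All this limits the damage, but the duration and restart figures are still reported as results.

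**Conclusion.** The point holds as a question of analysis choice and disclosure. If some NAJS users receive about three months' supply, recorded exposure is biased mainly downward: to about 33% of true days when all refills come at 90–92 days, about half when they vary around 90 days, and about 83–84% at a regular 84–89 days. Sparse one-month fills err upward, by up to 2.1 times in the example. First-treatment duration is the most sensitive measure, because one fill not followed within 89 days gives exactly 30 days by construction.

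Two stronger readings are not supported. A reader might infer that such a user loses two thirds of her cumulative dose; that follows only if NAJS dose is computed from inferred days, and the protocol does not give the NAJS dose formula. A reader might also infer that the before–after comparison is invalid; that needs supply length to change across the intervention, and nothing in the documents shows it. If it did change, the effect could be large: a move from 91-day to 30-day supplies with unchanged use would raise the recorded share from about 33% to 100%, opposite to the Table 11 hypothesis of lower duration and dose.

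Splitting episodes does not create false new users in Objectives 1 and 6, because the 365-day washout in section 8.8 prevents it.

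**What to change.** 1. Where NAJS records quantity, derive each prescription's length, and the cumulative dose, from quantity and strength.
2. Otherwise keep the 90/30 rule as primary and pre-specify a NAJS sensitivity analysis for Objectives 2 and 5 with a longer tail (for example 90 days) and a longer joining limit (for example under 120 days start to start). Four fills at 91 days would then give 3 × 91 + 90 = 363 of 364 days. With only the joining limit lengthened, four fills at 90 days give 3 × 90 + 30 = 300 of 360 (83%).
3. Report, for NAJS, the distribution of refill intervals and the share of users with a duration of exactly 30 days, by period. This shows whether the issue matters and whether supply length shifted.
4. State in section 11 that the error is mainly downward for longer supplies, and that restart counts and on-treatment meningioma are affected as well as duration and dose.

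Replacing the primary rule with a product-specific median refill interval is not advised: if most fills of a product are monthly, a limit of median plus 30 days would be about 60 days and would split users who are now joined.

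The cost is some protocol wording and one more run in one database, with no new data. The longer tail overstates exposure for one-month supplies (twelve monthly fills: 11 × 30 + 90 = 420 against 360 days), which is why it belongs in a sensitivity analysis.
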